#### Analysis

The hypothesis will be tested at the 5% significance level. The analysis will be carried out by calculating the 95% lower confidence bound (LCB) on the mean change in UPDRS part III motor examination score based on a t-distribution. The null hypothesis will be rejected if the 95% LCB is greater than 0.

## Clinical Investigational Plan

### 12.2 SAMPLE SIZE

The sample size is calculated assuming a success (therapeutic window of directional stimulation is larger than the one of omnidirectional stimulation) rate of 75%. [REDACTED]

### 12.3 PASS/FAIL CRITERIA TO BE APPLIED TO THE RESULTS OF THE CLINICAL STUDY

There are no pass/fail criteria to be applied to the results of this clinical study.

### 12.4 THE PROVISION FOR AN INTERIM ANALYSIS, when applicable

Masked interim analysis will be performed to compare distribution of therapeutic window at 3 months, and to compare UPDRS at 3 and 6 months. Group names will be masked. Masked analysis will also be performed for the subset of subjects enrolled at implant, and for the subset of subjects enrolled after implant. Additional unblinded interim analysis will be conducted after additional subjects reach 3 months of follow-up.

### 12.5 CRITERIA FOR THE TERMINATION OF THE CLINICAL STUDY ON STATISTICAL GROUNDS

There is no planned termination for the study based on statistical grounds.

### 12.6 PROCEDURES FOR REPORTING ANY DEVIATION(S) FROM THE ORIGINAL STATISTICAL PLAN

Any deviations from the statistical analysis plan will be documented.

### 12.7 THE SPECIFICATION OF SUBGROUPS FOR ANALYSIS

There will be a subgroup analysis of change in UPDRS part III motor examination score from 3 months to 6 months for the subset of subjects using omnidirectional stimulation at 3 months and directional stimulation at 6 months. Subject and clinician preference will be evaluated for the subset who have omnidirectional stimulation for the first 3 months and directional stimulation for the subsequent 3 months. There will also be a subgroup analysis of endpoints for the subset of subjects enrolled at implant, and for the subset of subjects enrolled after implant.

### 12.8 PROCEDURES THAT TAKE INTO ACCOUNT ALL THE DATA

Analyses will be performed in subjects who have evaluable therapeutic windows for both omnidirectional and directional stimulation for the primary endpoint and the first secondary endpoint. The analysis will be performed in subjects who have 3- and 6-month UPDRS part III motor examination

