### Clinical Investigational Plan

	
Total amount of time required for each study visit and programming. Long-term outcomes evaluated by change compared to baseline in UPDRS part III motor examination, UPDRS part II ADLs and PDQ-39, at the 36-month follow-up visit.

Design	
This study is designed as a prospective, blinded-subject, blinded-evaluator, observational, multi-center 36 month post market clinical follow up study. The total duration of this study is expected to be 60 months. The clinical study will be conducted at up to 60 centers in the European Union, United States, Latin America, and Australia. Up to 350 subjects will be enrolled. The primary endpoint analysis will be performed when 66 subjects have completed 12 months of follow-up and have evaluable primary endpoint at the 3-month follow-up visit. Interim annual progress reports will be reported to comply with Post-Market Clinical Follow-up (PMCF) requirements.
 
Baseline data can be collected from the subject’s medical records to compare to follow-up visits. Data will be collected 3, 6, 12, 24 and 36 months after initial programming for comparison to baseline.
 
A subset of subjects enrolled in this study will be used to meet the PMCF requirement for CE mark. Once this subset of subjects is enrolled and followed for 12 months and have evaluable primary endpoint at the 3-month follow-up visit, a report will be submitted indicating completion of this requirement.

Devices Used	
The following devices will be used in the study:
 
 
Infinity DBS System
 
Infinity DBS system including Implantable Pulse Generator (IPG), the 4 and 8 channel leads and accessories
 
Infinity Clinician Programmer App and Patient Controller App
 

Study Population	
Subjects who have a diagnosis matching the approved indication and are being considered for a DBS implant or who have been implanted with an Infinity system comprise the target population for this study. Subjects who meet all of the inclusion criteria and none of the exclusion criteria, and who have signed a statement of informed consent approved by an Ethics Committee (EC) or Institutional Review Board (IRB), will be enrolled in the study.
 
The PMCF requirement will be complete when 66 subjects have been followed for 12 months and have evaluable primary endpoint at the 3-month follow-up visit.

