##### Leads

St. Jude Medical DBS leads are designed for introduction into the brain using standard stereotactic neurosurgical techniques. Leads feature electrodes on a stiff distal end with an inactive lead tip. The proximal end of the lead contains contact bands that correspond with each of the distal electrodes and an inactive band that functions as a contact for a setscrew when connecting to a compatible extension. Additionally, the leads have colored bands that can help during implantation to differentiate between the right and left sides of the body. Two types of leads are available: 4 channel and 8 channel. The 4-channel leads contain cylindrical electrodes that provide stimulation in all directions around the lead. The 8-channel leads contain cylindrical and segmented electrodes. The segmented electrodes can be

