### 6-Month Follow-Up Visit (6 months ± 30 days since initial programming or consent date)

The following information will be collected at the 6-month follow-up visit:

- PDQ-39;
- UPDRS part II ADLs On Medication / On Stimulation;
- UPDRS part III motor examination On Medication/ Off and On Stimulation assessed by a blinded evaluator;
- Programming parameters; device session data;
- Subject and clinician preference;
- Unscheduled visits (if applicable);
- AE, system revision, and/or protocol deviation (if applicable).

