## Clinical Investigational Plan

The width of the therapeutic window is defined as the electrical current at which a sustained side effect appeared minus the electrical current at which a meaningful therapeutic benefit was obtained.

At the conclusion of the 3-month visit, the site physician should select the directional program that provides the best clinical benefit for the subject based on the detailed device testing that was completed and the subject should remain programmed using a directional configuration until the 6-month visit. If in the investigator's opinion, the directional configuration does not provide adequate therapy for the subject, the investigator may change the programming to allow the use of an omnidirectional configuration. Subjects who are implanted with the 4 channel lead will only have the omnidirectional testing at the initial programming visit to determine therapeutic window and first side effect. At the 3-month visit these subjects will complete the omnidirectional testing, will have the programming parameters collected and will complete the visit evaluations.

**12-Month Visit - Device testing is to be completed with the subject in the Off Medication state.** Omnidirectional and directional testing will be repeated according to the instructions above.

**36-Month Visit - Device testing is to be completed with the subject in the Off Medication state.** Omnidirectional and directional testing will be repeated according to the instructions above.

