### 12.0 STATISTICAL CONSIDERATIONS

#### 12.1 STATISTICAL DESIGN, HYPOTHESES, METHOD AND ANALYTICAL PROCEDURES

A subset of subjects enrolled in this study will be used to meet the Post Market Clinical Follow-Up (PMCF) requirement for CE mark. Once this subset of subjects is enrolled and followed for 12 months and have evaluable endpoint data at the 3-month follow-up visit, a report pertaining to primary endpoint and secondary endpoints analyses will be submitted indicating completion of this requirement.

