## Clinical Investigational Plan

complete for the second secondary endpoint. Subject accountability for enrolled subjects will be performed prior to analyses of the primary and secondary endpoints.

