### 12.12 TIMING FOR ANALYSES

The dataset will be frozen for analysis when 66 subjects have completed the 12-month visit and have evaluable primary endpoint at the 3-month follow-up visit to support the minimum requirements to meet the Post Market Clinical Follow-Up (PMCF) requirement for CE mark.

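### Section 12.8 sets no lead-type condition for secondary endpoint 2, so subjects with only 4-channel leads, who cannot receive directional stimulation, can enter the directional versus omnidirectional test

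*Combined protocol and SAP*

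**What the plan says.** Section 12.8 gives two analysis rules. The primary endpoint and secondary endpoint 1 need evaluable therapeutic windows in both stimulation modes. For secondary endpoint 2 the rule is different: "The analysis will be performed in subjects who have 3- and 6-month UPDRS part III motor examination" "complete for the second secondary endpoint". Completeness is its only condition.

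Section 12.1.2.2 defines the change as the month-3 score, labelled omnidirectional, minus the month-6 score, labelled directional. It rejects the null if the 95% lower confidence bound on the mean change, from a t-distribution, exceeds zero.

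The 4-channel lead is a study device: the synopsis lists "the 4 and 8 channel leads and accessories", and Appendix D gives model numbers for both types. Section 4.5.1 requires bilateral implants in the subthalamic nucleus and names no lead type. Section 5.1 says of the lead itself: "The 4-channel leads contain cylindrical electrodes that provide stimulation in all directions around the lead". Section 6.6 provides for subjects who have it. They get no directional testing, but "At the 3-month visit these subjects will complete the omnidirectional testing, will have the programming parameters collected and will complete the visit evaluations". The month-6 schedule lists "UPDRS part III motor examination On Medication/ Off and On Stimulation assessed by a blinded evaluator" with no exception for them.

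Section 12.7 plans the same UPDRS part III change in subjects who were in omnidirectional mode at month 3 and directional mode at month 6, as a subgroup.

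**The concern.** A subject with 4-channel leads on both sides satisfies the rule in 12.8 with two omnidirectional scores. The difference between them cannot reflect a change of mode. It holds whatever moved between months 3 and 6 (time, medication, reprogramming within omnidirectional mode) plus measurement error. The hypothesis is about directional stimulation, and such a pair carries no information on it.

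At stake is the estimate and the power of secondary endpoint 2. If scores do not drift over time, these pairs pull the mean change toward zero. The same paragraph avoids this for the primary endpoint and secondary endpoint 1 by requiring data in both modes, so those two analyses are unaffected.

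**Working it through.** **Can these subjects reach the test?** Eligibility does not exclude them (4.5.1). They complete the month-3 evaluations (6.6), which include UPDRS part III, and the month-6 UPDRS part III is scheduled for everyone. Section 12.8 asks for nothing more. Followed as written, the rule admits them.

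**Inputs.** From the documents: a one-sided 5% one-sample t test (12.1.2.2), and 66 as the count that triggers the data freeze (12.12). No effect size, standard deviation or sample size for this endpoint is visible, so there is no planned figure to reproduce. Assumed: standardised effect d of 0.20, 0.30 or 0.40 in subjects with a mode contrast; k subjects with only 4-channel leads and mean change 0; SD 1 within each group.

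**Formulas.** With m contrast subjects, n = m + k and s = k/n:

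- mean change = d(1 − s)
- SD = √(1 + s(1 − s)d²)
- noncentrality = √n × mean/SD
- power = P(noncentral t on n − 1 df exceeds the 95th percentile of central t)

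**Worked case, m = 66, d = 0.30.**

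- k = 0: noncentrality = 0.30 × √66 = 2.437, power 0.778.
- k = 7: n = 73 and s = 7/73 = 0.096. The mean is 0.30 × 0.904 = 0.271 and the SD is √(1 + 0.096 × 0.904 × 0.09) = 1.004. Noncentrality is √73 × 0.271/1.004 = 2.308 (from unrounded values), power 0.739.

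**Range, m = 66.**

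| k added | share s | d = 0.20 | d = 0.30 | d = 0.40 |
|---|---|---|---|---|
| 0 | 0 | 0.485 | 0.778 | 0.942 |
| 1 | 0.015 | 0.480 | 0.773 | 0.939 |
| 3 | 0.043 | 0.471 | 0.761 | 0.932 |
| 7 | 0.096 | 0.453 | 0.739 | 0.918 |
| 16 | 0.195 | 0.419 | 0.694 | 0.887 |

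At d = 0.30, adding 1, 3, 7 or 16 such subjects is equivalent to testing about 65, 63, 60 or 53 contrast subjects instead of 66. With an assumed 132 contrast subjects and d = 0.20, adding 6, 14 or 32 takes power from 0.739 to 0.722, 0.701 and 0.656.

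**Simulation, 200,000 replicates, d = 0.30.** For k = 0, 1, 3, 7 and 16, power was 0.780, 0.774, 0.763, 0.740 and 0.697, in line with the table. With no effect and no time change, type I error lay between 0.0495 and 0.0511.

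**Subjects with one lead of each type.** Suppose they keep half the effect (assumed). Adding 3, 7 or 16 of them to 66 at d = 0.30 gives power 0.779, 0.779 and 0.783, against 0.778 without them. The mean is multiplied by (1 − s/2). Excluding them gains no power.

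**The case against.** The best counter-argument is that the plan already excludes these subjects. Section 12.1 opens by tying the CE-mark report to subjects with evaluable month-3 endpoint data, and says that "a report pertaining to primary endpoint and secondary endpoints analyses will be submitted indicating completion of this requirement". Section 12.12 freezes the data "when 66 subjects have completed the 12-month visit and have evaluable primary endpoint at the 3-month follow-up visit". An evaluable primary endpoint needs a directional window, which a subject with only 4-channel leads cannot have. The labels in 12.1.2.2 point the same way: without a directional month-6 score, the change variable could be called undefined.

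This is a fair reading but not a settled one. Section 12.12 fixes when the data are frozen, and 12.1 describes a report. Section 12.8 is where the rule for each endpoint is stated, and it does not carry the limit over. The labels describe the intended schedule, while 6.6 lets investigators change mode. Section 12.7 implies that the main set is wider than actual switchers. That width could come from 8-channel subjects who changed mode, so it does not prove that 4-channel subjects are included. The text stays open.

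It is also true that the 12.7 subgroup gives an estimate free of these pairs, that 12.3 applies no pass/fail criteria, and that a study built around directional leads may enrol few or no such subjects. These facts keep the point small. They do not settle who enters the main test.

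A reader might infer more than the documents support:

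- **A raised false-positive rate.** With no time change, type I error stays at 5%. A time change shared by all subjects would be in the 8-channel pairs as well, so admitting 4-channel subjects does not create that problem.
- **A need for 8-channel leads on both sides.** Subjects with one lead of each type carry some contrast and can count as primary-endpoint successes, because 4.2 and 4.4.1 need only one lead with the wider directional window.

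**Conclusion.** The point holds as a minor one. As written, 12.8 admits to secondary endpoint 2 subjects who cannot receive the stimulation being tested. With no time change, the expected mean change shrinks by exactly their share, whatever the effect size. The power loss is modest: at an assumed effect of 0.30 with 66 contrast subjects, about 2 percentage points for 3 such subjects, 4 for 7 and 8 for 16. These figures rest on assumed effect sizes, counts and equal within-group SDs. The actual number of subjects with only 4-channel leads is not stated, and if it is zero there is no loss.

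**What to change.** In 12.8:

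1. Define the secondary endpoint 2 set as subjects with at least one 8-channel directional lead and complete 3- and 6-month UPDRS part III, whatever mode was in use at either visit.
2. Report subjects with only 4-channel leads descriptively.
3. Report the 12.7 omnidirectional-to-directional subset beside the main test as supportive, with counts of subjects by mode in use at months 3 and 6.

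This takes two or three sentences and no new data: lead data are collected at implant (6.5) and programming parameters at months 3 and 6 (6.2). Lead type is fixed at implant, before either score, so the restriction does not select on response to either mode. Subjects with a directional lead who changed mode for inadequate therapy stay in on purpose, because removing them could select on response. Some pairs without a contrast will therefore remain. The cost is slightly fewer subjects in the test.

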## Clinical Investigational Plan

complete for the second secondary endpoint. Subject accountability for enrolled subjects will be performed prior to analyses of the primary and secondary endpoints.

### 12.9 THE TREATMENT OF MISSING, UNUSED, OR SPURIOUS DATA, INCLUDING DROP-OUTS AND WITHDRAWALS

There are no plans to perform imputations for missing data, subject dropouts or withdrawals. If spurious data are discovered, these data will be excluded from analyses. Reasons for exclusion of any data from analyses will be summarized.

### 12.10 THE EXCLUSION OF PARTICULAR INFORMATION FOR THE TESTING OF THE HYPOTHESIS

There are no intent to exclude information for the testing of the hypothesis.

### 12.11 IN MULTI-CENTER STUDIES, THE MINIMUM AND MAXIMUM NUMBER OF SUBJECTS TO BE INCLUDED FOR EACH CENTER

A minimum of 1 subject may be included at each center participating in the study.

### 12.12 TIMING FOR ANALYSES

The dataset will be frozen for analysis when 66 subjects have completed the 12-month visit and have evaluable primary endpoint at the 3-month follow-up visit to support the minimum requirements to meet the Post Market Clinical Follow-Up (PMCF) requirement for CE mark.

### 13.0 DOCUMENT RETENTION

St. Jude Medical and the Principal Investigators will maintain the clinical study documents as required by St. Jude Medical, Inc. and applicable regulatory requirements. They will take measures to prevent accidental or premature destruction of these documents. The Principal Investigator or St. Jude Medical may transfer custody of records to another person/party and document the transfer at the investigational site or at St. Jude Medical's facility.

These documents must be retained by the investigational site for a period of 2 years after clinical study conclusion and made available for monitoring or auditing by St. Jude Medical's representative or representatives of the FDA and other applicable regulatory agencies. The Principal Investigator must ensure the availability of source documents from which the information on the case report forms was derived.

### 14.0 AMENDMENTS TO CLINICAL INVESTIGATIONAL PLAN

Study related documents such as, the Investigator Brochure (IB), Report of Prior Investigations (RPI), CIP, CRFs, Informed Consent form and other subject information, or other clinical study documents will be amended as needed throughout the clinical study, and a justification statement will be included with each amended section of a document. Proposed amendments to the CIP will be agreed upon between the Sponsor and the Steering Committee (if applicable). The Steering Committee is responsible for

## Clinical Investigational Plan

overseeing the scientific and operational aspects of the clinical investigation. This committee will meet regularly to monitor subject enrollment, general data collection and non-compliance with the CIP at individual centers, to review operational issues that may arise and warrant a CIP amendment or other corrective action and to determine policy regarding any publications arising from data generated from the performance of the clinical investigation.

The amendments to the CIP and the subject's Informed Consent will be notified to, or approved by, the EC or IRB and regulatory authorities, if required. The version number and date of amendments will be documented.

The amendment will identify the changes made, the reason for the changes and if it is mandatory or optional to implement the amendment.

Any amendment affecting the subject requires that the subject be informed of the changes and a new consent be signed and dated by the investigator at the subject's next follow up.

Changes to, or formal clarifications of, the CIP will be documented in writing and provided to the investigators. This information will be incorporated when an amendment occurs.

### 15.0 INVESTIGATION SUSPENSION OR TERMINATION

#### 15.1 PREMATURE TERMINATION OF THE WHOLE CLINICAL STUDY OR OF THE CLINICAL STUDY IN ONE OR MORE INVESTIGATIONAL SITES

The Sponsor reserves the right to stop the study at any stage, with appropriate written notice to the investigator.

Possible reasons for early termination of the study by the sponsor, either at local, national or international level, may include, but are not limited to:

- The device / therapy fails to perform as intended
- Occurrence of USADE which cannot be prevented in future cases
- Sponsor's decision
- Recommendation from DSMB to Steering committee and Sponsor
- Request from Regulatory bodies
- Request of Ethics Committee or Institutional Review Board
- Concern for subject safety and welfare
- Failure to secure subject Informed Consent prior to any investigational activity
- Failure to report unanticipated adverse device effects within 72 hours to St. Jude Medical and the EC
- Repeated non-compliance with this CIP or the Clinical Trial Agreement
- Inability to successfully implement this CIP
- Violation of the Declaration of Helsinki 2008 (refer to Appendix C)
- Violation of applicable national or local laws and regulations
- Falsification of data, or any other breach of ethics or scientific principles
- Loss of or unaccounted use of investigational device inventory

The study will be terminated according to applicable regulations.

## Clinical Investigational Plan

The investigator may also discontinue participation in the clinical study with appropriate written notice to the Sponsor.

Should either of these events occur, the investigator will return all documents to the sponsor; provide a written statement as to why the premature termination has taken place and notify the EC or IRB and/or the Competent Authority (if applicable). Follow-up for all enrolled subjects will be as per CIP requirements.

A Principal Investigator, EC or IRB or regulatory authority may suspend or prematurely terminate participation in a clinical study at the investigational sites for which they are responsible.

If suspicion of an unacceptable risk to subjects arises during the clinical study or when so instructed by the EC or IRB or regulatory authority, St. Jude Medical may suspend the clinical study as appropriate while the risk is assessed. St. Jude Medical will terminate the clinical study if an unacceptable risk is confirmed.

St. Jude Medical will consider terminating or suspending the participation of a particular investigational site or investigator in the clinical study if monitoring or auditing identifies serious or repeated deviations on the part of an investigator.

If suspension or premature termination occurs, the terminating party will justify its decision in writing and promptly inform the other parties with whom they are in direct communication. The Principal Investigator and St. Jude Medical will keep each other informed of any communication received from EC or IRB or regulatory authority.

If for any reason St. Jude Medical suspends or prematurely terminates the study at an individual investigational site, St. Jude Medical will inform the responsible regulatory authority, as appropriate, and ensure that the EC or IRB are notified, either by the Principal Investigator or by St. Jude Medical. If the suspension or premature termination was in the interest of safety, St. Jude Medical will inform all other Principal Investigators.

If suspension or premature termination occurs, St. Jude Medical will remain responsible for providing resources to fulfill the obligations from the CIP and existing agreements for following up the subjects enrolled in the clinical study, and the Principal Investigator or authorized designee will promptly inform the enrolled subjects at his/her investigational site, if appropriate.

